**Arterial stiffness:** cfPWV the non-invasive gold standard measurement of central arterial stiffness will be assessed using an applanation tonometry automatic device (NIHem, Cardiovascular Engineering Inc) with participants lying supine. Briefly, common carotid artery and femoral artery pressure waveforms will be recorded using a high-fidelity strain-gauge transducer placed separately on both arteries permitting pulse transit time estimation through the ECG R-wave to the foot of the applanation waves (intersecting tangent foot-to-foot method). PWV is then calculated by dividing carotid-femoral distance (subtraction method) by pulse transit time (26). Pulse waveforms velocity from carotid-brachial and radial artery tracts will also be measured and interpreted as regional indices of upper limb stiffness. All measurements will be conducted by reliable operators (i.e., CVs < 5%) on the right side of the body and ensuring that repeated measurements differ by less than < 0.5 m.s (27). Brachial waveforms and BP will be used to calibrate central pressure waveforms.

Local carotid stiffness and blood flow will also be measured from the common carotid artery using a high-resolution ultrasound (Arietta 750, Fujifilm, Tokyo, Japan) and high frequency (7.5 MHz) linear probe. Carotid artery diameter and blood velocity will be measured using the wave intensity mode with the probe placed on the skin over the carotid artery approximately 1-2 cm to the proximal carotid bifurcation with a 60-degree insonation angle. Carotid stiffness indices such as  $\beta$  stiffness (eq.1) and PWV (eq.2) will be estimated according to the manufacturer's formulas:

$$(eq. 1) \beta = \ln \left[ \frac{SBP/DBP}{(D_{syst} - D_{diast})/D_{diast}} \right]$$

Where,  $\beta$  is beta stiffness; SBP, brachial systolic blood pressure, DBP, diastolic blood pressure;  $D_{syst}$ , brachial artery diameter during systole;  $D_{diast}$ , brachial artery diameter during diastole.

$$(eq. 2) PWV = \sqrt{((\beta \times DBP)/(2\rho))}$$

Where, PWV is brachial artery pulse wave velocity;  $\beta$ , beta stiffness, DBP, brachial diastolic blood pressure; and  $\rho$ , is blood density - assumed constant (1050 kg/m^3).

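### Eq. 1 for carotid beta stiffness, as printed, does not fit eq. 2, and the legends name the wrong artery (minor; secondary index only)

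*Combined protocol and SAP*

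**What the plan says.** The Arterial stiffness text under Vascular function states: "Local carotid stiffness and blood flow will also be measured from the common carotid artery". It goes on: "Carotid artery diameter and blood velocity will be measured using the wave intensity mode". The resulting indices, beta (eq. 1) and PWV (eq. 2), "will be estimated according to the manufacturer's formulas".

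In the text as supplied, eq. 1 begins "\beta = \ln \left[ \frac{SBP/DBP}{(D_{syst} - D_{diast})/D_{diast" (markup, closing brackets left off here). The bracket after ln opens before the fraction and closes after it, so the logarithm covers the pressure ratio and the strain together. Eq. 2 is PWV = √(beta × DBP / (2ρ)), with ρ fixed at 1050 kg/m³.

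The legend to eq. 1 defines Dsyst as "brachial artery diameter during systole" and labels Ddiast in the same way. The legend to eq. 2 calls the result a brachial PWV.

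**The concern.** There are two separate defects.

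1. **Form of eq. 1.** Eq. 2 turns beta into a wave speed, which works only if beta measures how steeply pressure rises per unit of strain. In eq. 1 as printed, strain enters only through a logarithm, so its output is not that quantity.
2. **Artery.** The legends name the brachial artery for an index acquired at the common carotid. This conflict is with the carotid description just above the equations. It does not depend on where the bracket falls.

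At stake is whether the carotid index can be reproduced from the plan. If an analyst coded eq. 1 as printed, the error in beta would vary with both blood pressure and strain. It would not be a constant that cancels between visits, time points or sexes.

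**Working it through.** **Inputs from the documents.** Eq. 1, eq. 2 and ρ = 1050 kg/m³ come from Vascular function. The resting limit of 130/90 mmHg comes from Inclusion criteria and is used only to bound the pressures tried. The plan states no beta, carotid PWV or strain, so there is no figure of its own to reproduce.

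**Assumed inputs.** Strain e = (Dsyst − Ddiast)/Ddiast from 0.04 to 0.20; pressures from 105/65 to 129/89 mmHg; 1 mmHg = 133.322 Pa.

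**Step 1: what eq. 2 requires.** Let x be the strain at any point in the cycle and take P = DBP × exp(beta × x).
- At diastole (x = 0), dP/dx = beta × DBP.
- Lumen area is A = Ad(1 + x)², so dA/dx = 2Ad at diastole.
- Wave speed follows PWV² = (A/ρ)(dP/dA) = (Ad/ρ) × beta × DBP/(2Ad) = beta × DBP/(2ρ). This is eq. 2.
- Setting P = SBP at x = e gives SBP = DBP × exp(beta × e), so beta = ln(SBP/DBP)/e.

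**Step 2: round trip at 115/70 mmHg, e = 0.10.**
- Log on the pressure ratio only: ln(115/70)/0.10 = 0.4964/0.10 = 4.96. Put back: 70 × exp(0.4964) = 115 mmHg, as it must be.
- As printed: ln[(115/70)/0.10] = ln(16.43) = 2.80. Put back: 70 × exp(0.280) = 92.6 mmHg, not 115.

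**Step 3: a limiting case.** As SBP approaches DBP at a fixed strain, the artery stretches for almost no rise in pressure, so beta should approach 0. The printed form approaches ln(1/e), which is positive for any strain below 1.

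**Step 4: size at an assumed 115/70 mmHg.** PWV = √(beta × 70 × 133.322/(2 × 1050)) = √(4.444 × beta).

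| Strain | beta printed | beta = ln(SBP/DBP)/e | Error | PWV printed (m/s) | PWV consistent (m/s) | Error |
|---|---|---|---|---|---|---|
| 6% | 3.31 | 8.27 | −60% | 3.84 | 6.06 | −37% |
| 10% | 2.80 | 4.96 | −44% | 3.53 | 4.70 | −25% |
| 14% | 2.46 | 3.55 | −31% | 3.31 | 3.97 | −17% |

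The PWV error is smaller because of the square root: at 6% strain, 1 − √(3.31/8.27) = 37%.

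**Step 5: the wider range.** The extremes over the assumed grid are:
- 129/75 mmHg, e = 0.04: beta 3.76 printed against 13.56, 72% too low (PWV 47% too low).
- 129/89 mmHg, e = 0.20: beta 1.98 printed against 1.86, 7% too high (PWV 3% too high).

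So even the sign of the error depends on the assumed strain and pressure.

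**The case against.** **The bracket may be an extraction artefact.** Eq. 1 is a stacked fraction read from PDF by a program, and ln(SBP/DBP) over strain could be reassembled with the logarithm around everything. This stands as a reason to check the original page first. It does not touch the brachial labels, which are plain text.

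**The manufacturer's formulas govern.** Diameters are acquired in the ultrasound's wave intensity mode, and nothing says that the team will code eq. 1 by hand. A reader might infer that the carotid data will be biased. The documents do not support that: if the device software computes the indices, the printed equation may be only a transcription slip. The objection does not remove the conflict, because the two formulas printed under that attribution disagree with each other.

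**Other stronger readings that do not hold.**
- A reader might take a 30–60% shortfall as a general result for stiffness. It applies to beta only, and only under assumed pressures and strain.
- A reader might think the brachial labels contradict eq. 2. Its legend carries the same label; the conflict is with the carotid text. The labels play no part in the computed error.
- A reader might expect the brachial FMD diameters to be used by mistake. The FMD text names baseline and peak diameters, not systolic and diastolic ones, and the text before eq. 1 makes the carotid source clear.
- A reader might infer a loss of power. From 14% to 6% strain, beta moves by about 0.8 as printed (3.31 − 2.46) and 4.7 in the consistent form (8.27 − 3.55). These are different scales, and residual spread is compressed too. No loss of standardised effect has been shown.

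**Conclusion.** Both defects stand on the text as supplied: eq. 1 is inconsistent with eq. 2, and the legends name the brachial artery for a carotid measurement. The numerical harm is conditional on eq. 1 being coded as printed, and its size is conditional on strain and pressure values that the documents do not give. The 115/70 mmHg table is therefore an illustration, and the wider grid shows how far it can move.

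Severity is minor. Study main outcomes lists brachial BP, cardiac autonomic indices, FMD and cfPWV, and none of them uses eq. 1 or eq. 2; cfPWV comes from tonometric transit time. Local carotid beta and PWV are not on that list, and Table 1 does not name them. The sample size rests on SBP.

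**What to change.** 1. Check eq. 1 against the original page and against the manufacturer's documented form.
2. State it as beta = ln(SBP/DBP) / [(Dsyst − Ddiast)/Ddiast].
3. Relabel Dsyst and Ddiast as common carotid diameters, and the eq. 2 result as carotid PWV. This is needed whatever the check of the bracket shows.
4. Say whether the device software or the study team computes the indices. Before analysis, recompute beta and PWV for a few scans from the recorded pressures and diameters, and confirm that the exported values match.

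The cost is one equation, the two legends and one check of exported values. No new data are needed, and neither the sample size nor the analysis of the main outcomes changes.

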#### Body composition

Participants will seat for 5-min inside the Bod Pod, (Body Composition System; Life Measurement, Incorporated, Concord, CA), a large egg-shaped chamber to have their body composition measured via air plethysmography. Participants will enter the Bod Pod only wearing minimal clothing (briefs for males and swimsuit for females), a swim cap and will be asked to breathe normally for 20-s and then into an internal breathing tube to measure thoracic gas volume.

This will permit the estimation of body density needed to calculate % of body fat via the Siri equation (28). The Bod Pod will be calibrated before each test following the manufacturer's instructions with the chamber empty while using a cylinder of known volume (50 L).

### Pulsatile hemodynamics and wave separation analysis

#### Pulsatile hemodynamics and wave separation analysis

Aortic impedance will be measured following the method outlined by Mitchell et al (29,30).

Aortic impedance describes pulsatile flow and pressure relations at the proximal aorta in early systole before the return of reflected waves. Firstly, 2D parasternal long-axis images of the left-ventricular (LV) outflow tract will be acquired using a 2-4-Mhz ultrasound transducer (Arietta V750, Fujifilm, Tokyo, Japan). This will permit the determination of aortic diameter defined as the largest diameter in early systole close to the aortic leaflets. Then, a 2-MHz continuous echo Doppler flowmeter (pedof) probe (Arietta V750, Fujifilm, Tokyo, Japan) will be placed at the suprasternal notch to estimate aortic flow as the product of blood velocity and LV outflow tract area. Lastly, carotid pressure waveforms will be acquired via applanation tonometry (NIHem, Cardiovascular Engineering Inc). Both aortic flow and carotid pressure signals will be integrated into the NIHem software to estimate aortic impedance as the ratio of carotid pressure by aortic flow. In addition, waveforms will be separated into forward (Pf) and backward waves (Pb) with their ratio considered an index of general wave reflection, using the NIHem software as previously described (30).

### Follow up

This study will not have a follow-up.

## Data Analysis Plan

### Data integrity

All study procedures described in this protocol will be performed by trained personnel and all raw data will be checked within the same day of the visit by the research team who collected it. Biweekly examinations of the analyzed data will be performed by the PI to ensure high-quality analysis is being performed.

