#### Isometric handgrip training intervention and control

Participants will train three days per week at home for 1 month using a reliable and validated digital handgrip dynamometer (DynX, MD System, Inc., Westerville, OH, USA)) in a seated position. The isometric handgrip training protocol will consist of four sets (2 for each hand) of two-min sustained contractions starting at 30% MVC interspersed by 1-min resting periods (a total of 12-min). All training sessions will be remotely supervised via Zoom or phone call by a research team member to ensure compliance with the exercise prescription. Before each training session, MVCs will be re-assessed over three repetitions, each separated by 30-s, to ensure an accurate exercise prescription (13). The highest value will be used to determine the target intensity of the session. In the control/washout conditions, participants will be instructed to maintain their normal daily routines.

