### *Cardiac autonomic function*

We will place electrodes directly on the skin of each participant to obtain the ECG trace required to estimate both heart-rate variability and baroreflex sensitivity outcomes.

**Heart rate variability and baroreflex sensitivity:** R-R intervals will be sampled at 1000 Hz frequency to obtain digital R waves digital sequences using the single ECG lead module of PowerLab data acquisition system (ADInstruments, BellaVista, NSW, Australia). All data acquisition and offline analyses will be conducted following the standards of the Task Force of the European Society of Cardiology and the North American Society of Pacing and Electrophysiology (17). Offline heart rate variability (HRV) analyses will be performed over a 2-min time series for each time-point (i.e., baseline, during and 5, 30 and 60 min after exercise) using the HRV analysis module of Lab Chart 8 (ADInstruments, BellaVista, NSW, Australia) (18). Main time-domain indices of interest include the standard deviation of NN intervals (SDNN) – a measure of overall variability, and the root mean square of the sum of the squares of the differences between NN intervals (RMSSD) – a measure of cardiovagal modulation. In addition, non-linear time-domain parameters will be derived from the Poincaré plot, including the vertical deviation that reflects mainly cardiovagal modulation (SD1), the longitudinal deviation (SD2), and the non-linear ratio SD1/SD2 an index of autonomic balance analogous to LF/HF ratio (19). The time-frequency domain analysis will be conducted using the Lomb-Scargle Periodogram, which permits accurate estimation of low (0.04 to 0.15 Hz) and high-power frequency (HF) power bands (0.15 to 0.40 Hz) in absolute and normalized power units during exercise conditions. Cardiac baroreflex sensitivity (BRS) will be estimated via the spontaneous sequence method over 2 min through the Lab Chart 8 baroreflex macro. Briefly, this method identifies ramps where increases in SBP ( $> 1$  mmHg) are coupled with increases of the RR interval ( $> 4$  ms) (linearly correlated) that occur over at least 3 beats (minimum sequence). The minimum acceptable correlation coefficient between SBP and RR interval ramps will be 0.80. Then, baroreflex sensitivity is estimated as the average of all regression slopes between the SBP and RR interval.

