### *Vascular function*

During the vascular function measurements, we will ask participants to lie quietly in the supine position. They will also experience a forearm occlusion to permit the assessment of endothelial function.

**Endothelial function:** will be non-invasively assessed via brachial artery FMD, which represents nitric oxide-dependent vasodilation and closely correlates with the endothelial function of the coronary arteries (20,21). FMD will be assessed in the right brachial artery with an ultrasound (Arietta V750, Fujifilm, Tokyo, Japan) equipped with a 7.5-MHz linear array probe incorporating a 5-MHz Doppler transducer, placed  $\sim 4$  cm above the antecubital fossa, and held by a stereotactic clamp following standard guidelines (22,23). Reactive hyperemia will be induced by rapid cuff deflation following a forearm occlusion (Hokanson SC10, Bellevue, WA 98005, USA) maintained for 5-min at 250 mmHg. Changes in intraluminal brachial artery diameter will be tracked with automated edge-detection software (FMD studio, Quipu srl, Pisa, Italy) allowing precise measurement of the artery diameter (23). Doppler measurements of peak hyperemic blood velocity with an insonation angle of  $\leq 60^\circ$  will allow calculation of FMD main stimuli - shear rate as  $(4 \times \text{peak blood velocity} / D_{\text{baseline}})$  (23). All FMD analyses will be done offline using the FMD studio. FMD will be presented both as an absolute change ( $\text{FMD (mm)} = D_{\text{peak}} - D_{\text{baseline}}$ ) and as a relative change ( $\% \text{ FMD} = (D_{\text{peak}} - D_{\text{bas}}/D_{\text{baseline}}) \times 100$ ) in diameter. If a non-linear ratio between  $D_{\text{peak}}$  and  $D_{\text{bas}}$

is observed (B coefficients < 1), %FMD will be allometrically scaled for  $D_{baseline}$  (24,25). In addition, blood flow will be estimated as (Mean blood velocity) x (Brachial Cross-Sectional Area) x (60). Brachial artery blood flow will be measured in both exercising and non-exercising arms. All FMD scans will be conducted by the same researcher with inter-day measurements CV <15% (22,23).

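### The plan describes no masking of whoever scores the offline FMD, HRV, baroreflex and beat-to-beat BP data, so reading choices could differ between training and control

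*Combined protocol and SAP*

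**What the plan says.** **Checking.** Under Data integrity, "all raw data will be checked within the same day of the visit by the research team who collected it". The next sentence adds a second look: "Biweekly examinations of the analyzed data will be performed by the PI". Neither step is described as masked, and the section does not name the person who scores.

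**Knowledge of condition.** Under Isometric handgrip training intervention and control, "All training sessions will be remotely supervised via Zoom or phone call by a research team member". The comparator is open: "In the control/washout conditions, participants will be instructed to maintain their normal daily routines". Nothing separates the people who supervise training from those who collect or score outcomes.

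**Offline scoring.** For vascular function, "All FMD analyses will be done offline using the FMD studio". For autonomic function, "Offline heart rate variability (HRV) analyses will be performed over a 2-min time series for each time-point", and the same paragraph refers to offline analysis for heart rate variability and baroreflex sensitivity together. The Blood pressure section has beat-to-beat pressure averaged offline over 2 to 5 min.

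**Limits on discretion.** For FMD, "Changes in intraluminal brachial artery diameter will be tracked with automated edge-detection software", and "All FMD scans will be conducted by the same researcher with inter-day measurements CV <15"%. Baroreflex sequences are picked by a software macro with numerical thresholds. cfPWV has a repeatability limit of 0.5 m/s.

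The design statement in the Research protocol section lists randomisation, control, cross-over and repeated measures. Masking of operators, readers, principal investigator or analyst is not mentioned there or elsewhere.

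**The concern.** Participants cannot be blinded to whether they trained, and the research team is in contact with them at every training session. If the person who scores a recording knows that it follows training, any choice left open at scoring can be made differently, even unintentionally, from the choice made on a control recording.

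The cross-over does not protect against this. Random order balances period effects, but an error that travels with the condition stays in the within-participant difference. Training condition is a fixed effect in the Statistical analysis section, so the error would be read as a training effect.

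**Working it through.** No figure in the plan bears on this point, so there is none to reproduce. The check sets the sections side by side.

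**Step 1. Which main outcomes are documented as scored offline?** Study main outcomes lists seven: SBP, DBP, RMSSD, HF, baroreflex sensitivity, FMD and cfPWV.

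| Outcome | Offline scoring documented? | What limits discretion | What stays open |
|---|---|---|---|
| RMSSD, HF | Yes (Cardiac autonomic function) | Software module, cited standards | Which 2 min is scored |
| Baroreflex sensitivity | Yes (same paragraph) | Macro: SBP > 1 mmHg, RR > 4 ms, at least 3 beats, r at least 0.80 | Which 2 min the macro is run on |
| FMD | Yes (Vascular function) | Automated edge detection | Reader not named; no rule for rejecting a scan |
| cfPWV | No | Automatic device; repeats within 0.5 m/s | Whether waveforms are re-read after the visit |
| Cuff SBP, DBP | No | Automated cuff, 4 mmHg rule, mean of last two | Nothing at the reading stage |

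The count is 2 + 1 + 1 = 4 of 7. Beat-to-beat finger BP is a further offline measure. The cuff is described for before and after exercise only, so the finger record appears to be the only described source of BP during the bout.

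**Step 2. Is there real discretion?** Table 1 allots 5 min to the block holding BP, arterial stiffness and autonomic function at rest and at 5, 30 and 60 min. HRV and baroreflex sensitivity use 2 min. No rule says which 2 min. For beat-to-beat BP the window may run from 2 to 5 min, so its length is open too. The baroreflex thresholds apply only after a window has been chosen.

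**Step 3. Where would a reading bias go?** Write b_T and b_C for the average reading error in training and control recordings. Then

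observed difference = (μ_T + b_T) − (μ_C + b_C) = true difference + (b_T − b_C).

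Randomising the order leaves b_T − b_C untouched. It is zero by design only if the reader cannot tell the conditions apart.

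**Step 4. Can a size be given?** The documents give no reader agreement by condition. As an illustration with assumed values (reading shift 0.02 mm, artery 3.5 to 4.0 mm, true FMD 6%):

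- Shift in both diameters: 0.21/3.52 = 5.97% and 0.24/4.02 = 5.97%, against 6.00%. The change is about 0.03 percentage points.
- Shift in peak diameter only: 0.02/3.5 = 0.57 and 0.02/4.0 = 0.50 percentage points.

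The answer depends almost wholly on how the error falls, and even the second case biases the contrast only if the shift also differs by condition. No size can be claimed.

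**The case against.** The strongest reply is that the Data integrity sentence describes same-day quality control of raw data, not scoring, and that absence of masking is inferred from silence. The plan says only that a team member supervises training; it does not say that this person scans or scores. The principal investigator reviews the analysed data. Baroreflex sequences are accepted by fixed rule, and FMD is the difference between two diameters tracked by software. SBP, on which the sample size is based, is also taken by automated cuff with an acceptance rule.

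Much of this stands, and it narrows the point. The sentence does not show that a condition-aware person scores. It shows that the plan as written allows it, with no step to prevent it. The principal investigator's review is a second check, but it is not described as masked. Automation acts after a window or scan has been selected.

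A further limit is that a reading bias equal in men and women cancels from the sex-by-training contrast, and one constant over time points cancels from the time-by-training contrast. The overall training contrast has no such protection, and nothing assures either equality.

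A reader might also infer that cfPWV is exposed in the same way, making five of seven outcomes. The Arterial stiffness paragraph does not describe offline scoring, so that count is not supported.

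**Conclusion.** The point holds as a risk of bias at the reading stage. Under the plan as written, four of the seven main outcomes, plus offline beat-to-beat BP, may be scored by someone who knows the condition at visits 2 and 3, with at least the choice of analysis window left open. This rests on two inferences: that silence on masking means none is planned, and that a team supervising all training will generally know who has just trained.

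Three stronger readings should be resisted:

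- **That the bias favours training, or is worth about half a percentage point of FMD.** The documents give no direction or size, and the half-point figure needs an assumed error in one diameter only that also differs by condition.
- **That masked scoring would remove the problem.** It does not reach choices made at acquisition, such as probe placement or repeating a tonometry reading, nor participant expectation.
- **That it is free.** Recoding takes staff time and delays scoring.

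It is a worthwhile, inexpensive improvement, not a flaw that invalidates the design.

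**What to change.** In Data integrity, with a matching line in the outcome sections:

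1. Limit the same-day check to signal completeness and quality.
2. Have an existing team member who does not score recode the files to hide participant, visit and condition.
3. Score FMD, HRV, baroreflex and offline beat-to-beat BP files in random order. Include any tonometry waveforms selected or re-read after the visit.
4. State in advance which 2 min is scored, the length of the beat-to-beat BP window, and when a recording is rejected.
5. Run the principal investigator's biweekly review on the coded files.
6. Unmask only when the dataset is locked.

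The cost is recoding time and a short delay in scoring and in the principal investigator's review. If files were held until each participant's last visit, the wait for baseline files would approach the stated 2 months of participation; batches mixed across participants would shorten it. No added visit, device or procedure is needed. If masked scoring is already intended, a sentence saying so and naming the scorer's role would settle the masking question.
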